8.2.7. Serum PSA

Serum PSA samples are scheduled at the screening visit, and at each Month 6, Month 12, and Month 24 (or end of treatment) visits. Total PSA (absolute values, change from baseline values, and percentage change from baseline values) will be summarized by visit and treatment group using both the LOCF and At Visit approaches. Change from baseline total PSA will be compared in terms of combination treatment versus tamsulosin treatment at each scheduled post-baseline assessment using a general linear model with effects for treatment and baseline total PSA.

Listings of PSA data will be produced. A listing of PSA data will be provided, along with a listing of PSA data exceeding the upper limit of normal.

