2.2. Study Objective(s) and Endpoint(s)

Objectives	Endpoints
Primary Objectives	Primary Endpoints

 To assess the efficacy of combination treatment with dutasteride 0.5mg and tamsulosin 0.2mg once daily in providing superior symptomatic improvement in subjects with BPH compared with once daily tamsulosin 0.2mg monotherapy after 2 years of treatment 	
 Change in IPSS from baseline at Year 2.
Secondary Objectives	Secondary Endpoints

 To assess efficacy and safety of combination treatment with dutasteride 0.5mg and tamsulosin 0.2mg including the clinical outcomes of AUR or BPH-related prostatic surgery compared with tamsulosin 0.2mg monotherapy after 2 years of treatment. 	
Efficacy
 
 Percent change in prostate volume from baseline Proportion of subjects with IPSS improvement of ≥ 2 points and ≥ 3 points from baseline and, separately, $\geq 25\%$ improvement from baseline Change in Qmax from baseline Proportion of subjects with Qmax improvement of $\geq 3\text{mL/sec}$ and, separately, $\geq 30\%$ improvement from baseline Time to event/ proportion of subjects with AUR or BPH related prostatic surgery Time to event/proportion of subjects with AUR Time to event/proportion of subjects undergoing BPH related prostatic surgery 
Health Outcome Measures
 
 Change in BPH-Related Health Status (Q8 of IPSS) from Baseline Change in BPH Impact Index (BII) from Baseline

Objectives	Endpoints
	
 Change in Problem Assessment Scale of the Sexual Function Inventory (PAS-SFI), from Baseline Resource Use related to AUR and BPH-related surgical events. 
Safety
 
 Adverse Events Change in total serum PSA from baseline Vital signs Post-void residual volume Clinical laboratory measurements (including haematology, chemistry) Physical examination: digital rectal examination (DRE) and qualitative breast examination Suicidality (C-SSRS)
Exploratory Objectives	Exploratory Endpoints

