4.1.3. Deviations which Require Exclusion from the Per-Protocol Population

In accordance with SOP-130050 and the ARI114265 PDMP, deviations which require exclusion from the Per-Protocol population should be identified; the 19 deviations are listed in the below table. The historical term used to describe these deviations in ARI114265 protocol is 'major'. In this RAP and for future reporting the phrase 'deviations which require exclusion from the Per-Protocol population' will replace 'major'.

Number	Deviations which Require Exclusion from the Per-Protocol Population
01	Missed placebo run-in phase
02	Incorrect study drug (wrong treatment) consumed
03	Randomized but did not consume double-blind study drug
04	Cumulative study drug compliance <75%
05	Cumulative study drug compliance >125%
	Violation of Inclusion Criteria (protocol #)
06	Confirmed BPH clinical diagnosis (Inclusion 2)
07	IPSS ≥12 at Screening (Inclusion 3)
08	Prostate volume ≥30cc by TRUS at Screening (Inclusion 4)
09	PSA ≥1.5ng/ml and ≤10ng/mL at Screening (Inclusion 5)
10	Qmax >5 mL/sec and ≤15mL/sec with Voided Volume ≥125mL/sec at Screening (Inclusion 6)
	Violation of Exclusion Criteria (protocol #)
11	Any conditions other than BPH, which may in the judgement of the investigator, result in urinary symptoms or changes in flow rate (Exclusion 6)
12	Use of 5ARI within 6 months of Screening or historical TRUS and throughout the study (Exclusion 10a)
13	Use of anabolic steroids within 6 months of Screening and throughout the study (Exclusion

Number	Deviations which Require Exclusion from the Per-Protocol Population
	10b)
14	Use of phytotherapy for BPH within 2 weeks of Screening and throughout the study (Exclusion 10c)
15	Use of alpha-adrenoreceptor blockers within 2 weeks of Screening and throughout the study, except study meds (Exclusion 10d)
16	Use of alpha-adrenoreceptor agonists or anticholinergics or cholinergics within 48 hours prior to all uroflowmetry and IPSS assessments (Exclusion 10e)
17	Use of selective beta 3-adrenoreceptor agonist (mirabegron) within 2 weeks prior to all uroflowmetry and IPSS assessments (Exclusion 10f)
18	Prohibited medications and non-drug therapies of Protocol Section 6.2 and not otherwise classified above.
	Other
19	Any condition which should exclude a subject from the Per-Protocol population which is not included above; identified by Study Team.

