7.1.2. Planned Primary Efficacy Statistical Analyses

Endpoint: The primary efficacy parameter is the change from baseline IPSS at Year 2 (Month 24) using the last observation carried forward approach (LOCF) based on the Intent-to-Treat (ITT) population.

[Table 3](#) provides an overview of the planned IPSS summaries and primary efficacy analyses. A list of planned data displays is in [Appendix 15](#): List of Data Displays.

Baseline and change from baseline are defined in [Appendix 6](#). Last observation carried forward (LOCF) and At Visit approaches are defined in [Appendix 7](#).

Note: IPSS timepoints earlier than Month 24, specifically Month 21 – Month 3, in this order, are classified as secondary endpoints. Summaries and analyses of these timepoints will be conducted in same manner and on same outputs as the primary analyses.

Reference [Table 4](#).

Model Specification and Results Presentation: Change from baseline IPSS at each scheduled post-baseline assessment will be compared in terms of combination treatment versus tamsulosin treatment using t-tests from a general linear model (GLM) with effects for treatment, cluster, and baseline IPSS. Two-sided tests at 0.05 level of significance will be conducted.

The adjusted mean estimates (mean and standard error), the adjusted mean difference, and the 95% confidence interval in terms of the adjusted mean difference will be presented. The adjusted mean difference will be in terms of combination treatment minus tamsulosin treatment. The model results will be presented on same tabular summary as the arithmetic mean, standard deviation, median, minimum and maximum. The results will be presented by treatment for each scheduled post-baseline assessment.

IPSS adjusted mean change from baseline will be plotted by treatment for each post-baseline scheduled visit in terms of each LOCF and At Visit approach.

Multiple Comparisons and Multiplicity: Reference [Appendix 11](#), Multiple Comparisons and Multiplicity.

Model Checking and Diagnostics: Reference [Appendix 12](#), Model Checking and Diagnostics for Statistical Analyses.

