8.1.3. Prostate Volume

Prostate dimensions are measured at the second screening visit (1b) and at each Month 12 and Month 24 (or end of treatment) visits. For analysis and reporting,

- Prostate Volume =
 $\pi/6$ (Anteroposterior Width x Cephalocaudal Width x Transverse Width).

Prostate volume percentage change from baseline is a secondary efficacy endpoint.

[Table 4](#) provides an overview of the planned prostate volume summaries and analyses. A list of planned data displays is in [Appendix 15](#): List of Data Displays. Baseline, change from baseline, and percentage change from baseline are defined in [Appendix 6](#). Last observation carried forward (LOCF) and At Visit approaches are defined in [Appendix 7](#). Summaries and analyses will be in terms of the ITT population; LOCF approach will be considered primary. Prostate volume summary statistics will be presented for baseline, Month 12 visit, and the Month 24 visit; change from baseline and percentage change from baseline summary statistics will be presented for the Month 12 and Month 24 visits.

Combination treatment and tamsulosin treatment will be compared in terms of prostate volume percentage change from baseline at the Month 12 and Month 24 visits using t-tests from the following general linear model; two-sided tests at 0.05 level of significance will be conducted:

- $\log(\text{post baseline prostate volume} / \text{baseline prostate volume}) = \log(\text{baseline prostate volume}) + \text{treatment} + \text{cluster}$

The adjusted mean estimates (mean and standard error), the adjusted mean difference, and the 95% confidence interval in terms of percentage change from baseline will be reported. The adjusted mean differences will be in terms of combination treatment minus tamsulosin treatment. The model results will be presented on same tabular summary as the arithmetic mean, standard deviation, median, minimum and maximum. The results will be presented by treatment for each scheduled post-baseline assessment.

Prostate volume adjusted mean percentage change from baseline will be plotted by treatment for each post-baseline scheduled visit in terms of each LOCF and At Visit approach.

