11.12. Appendix 12: Model Checking and Diagnostics for Statistical Analyses

Endpoint(s)	IPSS change from baseline
Analysis	General Linear Model

Assessments of the general linear model residuals will be performed. These assessments will include reviews of residual by predicted value plots and normal probability plots on residuals. This will be in terms of the change from baseline IPSS at Month 24 using the LOCF and At Visit approaches. Similar assessments of other time periods will not be reported unless dictated by substantive findings.If these assumptions are not met, appropriate non-parametric analyses will be performed to test the robustness of the results of the parametric analyses. If non-parametric analyses are performed further detailed information will be provided in the Statistical Appendix for the Clinical Report.The interaction of cluster with treatment will be assessed by adding the (interaction) term to the above planned analysis model at Month 24.The interaction of baseline IPSS with treatment will be assessed by adding the (interaction) term to the above stated model at Month 24.The effects of baseline subgroups and their interactions with treatment will also be assessed. This is described in Appendix 10, Examination of Covariates and Subgroups	

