3.76 3.70	Summary of Shift in Laboratory Values: Normal or Low at Baseline to High at Any Time Post-Baseline
3.77 3.71	Summary of Shift in Laboratory Values: Normal or High at Baseline to Low at Any Time Post-Baseline
3.78 3.72	Summary of Laboratory Data Transitions: Change From Baseline to Final Assessment
3.79 3.73	Summary of Baseline Threshold Laboratory Values
3.80 3.74	Summary of Threshold Laboratory Values at Any Time Post-Baseline
3.81 3.75	Summary of Baseline Total PSA Values (ng/ml)
3.82 3.76	Summary of Total PSA (ng/ml) at Post-Baseline Visits (LOCF)
3.83 3.77	Summary of Total PSA (ng/ml) at Post-Baseline Visits (At Visit)
3.84 3.78	Summary of Total PSA Change From Baseline (ng/ml) (LOCF)
3.85 3.79	Summary of Total PSA Change From Baseline (ng/ml) (At Visit)
3.86 3.80	Summary of Total PSA Percentage Change From Baseline (LOCF)
3.87 3.81	Summary of Total PSA Percentage Change From Baseline (At Visit)
3.88 3.82	Summary of Post-Void Residual Volume at Screening and Baseline
3.89 3.83	Summary of Post-Void Residual Volume at Each Post-Baseline Visit (LOCF)
3.90 3.84	Summary of Post-Void Residual Volume at Each Post-Baseline Visit (At Visit)
3.91 3.85	Summary of Post-Void Residual Volume Change from Baseline (LOCF)
3.92 3.86	Summary of Post-Void Residual Volume Change from Baseline (At Visit)
3.93 3.87	Summary of Post-Void Residual Volume Percentage Change from Baseline (LOCF)
3.94 3.88	Summary of Post-Void Residual Volume Percentage Change from Baseline (At Visit)
3.95 3.89	Summary of Gynecomastia Evaluation
3.96 3.90	Summary of Change from Baseline Gynecomastia Evaluation
3.97 3.91	Summary of Digital Rectal Examination

Safety	
3.98 3.92	Summary of Change from Baseline Digital Rectal Examination
3.99 3.93	Summary of Vital Signs
3.100 3.94	Summary of Change from Baseline Vital Signs
3.101 3.95	Summary of Vital Signs Exceeding Threshold at Baseline
3.102 3.96	Summary of Vital Signs Exceeding Threshold at Any Post-Baseline Visit
3.103 3.97	Summary of C-SSRS Data
3.104 3.98	Listing of C-SSRS Data for Subjects With Suicidal Ideation and/or Behavior

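### PSA is compared between arms only as raw ng/mL change, in the one pooled general linear model without cluster; percentage change gets no adjusted estimate or interval

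*SAP*

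**What the plan says.** Section 8.2.7 compares PSA change from baseline at each scheduled post-baseline assessment "using a general linear model with effects for treatment and baseline total PSA". There is no transformation and no cluster term. For the other scale, section 8.2.7 says only that absolute values, changes and "percentage change from baseline values) will be summarized by visit and treatment group using both the LOCF and At Visit approaches". The displays for this are Tables 3.80 and 3.81; the first is titled "Summary of Total PSA Percentage Change From Baseline (LOCF".

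Section 2.2 lists the endpoint, under Safety, as "Change in total serum PSA from baseline". The entry range appears in section 4.1.3: "PSA ≥1.5ng/ml and ≤10ng/mL at Screening (Inclusion 5").

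Elsewhere the plan works differently. The primary analysis in section 7.1.2 uses a "general linear model (GLM) with effects for treatment, cluster, and baseline IPSS". For prostate volume, section 8.1.3 says the arms "will be compared in terms of prostate volume percentage change from baseline", through a model for the log of the post-baseline to baseline ratio with log baseline, treatment and cluster. Appendix 12 states that "Assessments of the general linear model residuals will be performed" for IPSS. Sections 8.1.3 and 8.1.4 extend those checks to prostate volume and Qmax.

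**The concern.** Two features of the PSA comparison are unexplained.

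- **Cluster.** It is missing from this model only. Section 9 removes cluster from the within-country models, which implies that it belongs in the pooled ones.
- **Scale.** PSA is positive and the entry range is wide, yet the only planned inference is a single ng/mL difference. If the treatment effect varies with starting PSA, that difference describes few individual men well, and the percentage-change tables offer no adjusted contrast or interval to put beside it.

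The treatment-by-baseline check in Appendix 12, which would show whether the ng/mL effect varies with baseline, is not extended to PSA. What is at stake is how well the PSA effect is described and, under some assumptions, how precisely it is estimated.

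**Working it through.** **1. Cluster across the plan's comparisons**

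| Comparison | Section | Cluster |
|---|---|---|
| IPSS | 7.1.2 | yes |
| Prostate volume | 8.1.3 | yes |
| Qmax | 8.1.4 | yes |
| BII, BHS, PAS SFI | 8.3.1 to 8.3.3 | yes |
| MMRM | Appendix 13 | yes |
| Post void residual (van Elteren test) | 8.2.8 | yes |
| PSA | 8.2.7 | no |

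PSA is the only pooled general linear model without it.

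**2. Inputs.** From the SAP: entry PSA 1.5 to 10 ng/mL, 1:1 allocation, four country clusters. Appendix 2 schedules PSA at Visit 1a and not at Visit 2, so the screening range is in effect the baseline range. The SAP gives no PSA standard deviation, expected effect or country difference, so there is no figure to reproduce. Everything below marked as assumed is not from the SAP.

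**3. Spread of effects if proportional.** With an assumed common ratio r, change = baseline × (r − 1). At r = 0.5:

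- baseline 1.5: 1.5 × (−0.5) = −0.75 ng/mL
- baseline 3: 3 × (−0.5) = −1.5 ng/mL
- baseline 10: 10 × (−0.5) = −5.0 ng/mL

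The extremes differ by 5.0/0.75 = 6.7-fold, which is the entry range 10/1.5. In simulation at r = 0.5 the section 8.2.7 model reports about −1.9 to −2.3 ng/mL.

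**4. Precision if proportional.** Simulated trials, all assumed: 300 per arm; log-normal baseline with median 3.2 and log SD 0.55, cut to 1.5 to 10. Efficiency is the squared ratio of the mean z statistics, section 8.2.7 model over log-ratio model with log baseline and cluster. At residual log SD 0.35:

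| Ratio | No country differences | Country log SD 0.1 | Country log SD 0.2 |
|---|---|---|---|
| 0.9 | 77% | 73% | 64% |
| 0.7 | 71% | 67% | 58% |
| 0.5 | 58% | 55% | 47% |

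That is roughly 45% to 75%. Over a wider grid (ratios 0.4 to 0.9, log SD 0.2 to 0.6) the range is 26% to 80%. The column with no country differences shows the cost of scale alone.

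**5. Cluster alone.** Comparing the raw model with and without cluster, the loss is nil when countries do not differ. It is at most about 27% (ratio 0.9, log SD 0.2, country log SD 0.2).

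**6. The opposite case.** Under an assumed additive effect of −1.5 ng/mL with SD 1.0, mean z is −18.40 for the raw model and −13.91 for the log-ratio model with cluster: (18.40/13.91)² = 1.75 in favour of the raw model. Before flooring, about 10% of treated values in that setting would be zero or negative, so it is an extreme one. A smaller additive effect of −0.5 ng/mL still favours the raw model, by about 1.5 to 1.6.

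**7. Effect on the test.** At ratios 0.4 to 0.5, mean |z| is at least 10 in every setting, so the conclusion is the same under either model. At ratio 0.9 with log SD 0.6 it could differ: about 1.7 to 1.8 for the raw model against 2.1 to 2.2 for the log-ratio model with cluster.

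**The case against.** The strongest reply is that each model follows its own listed endpoint. Section 2.2 names change for PSA and percent change for prostate volume, so the different scales are not a contradiction. This stands, and it is why the ng/mL comparison should be kept.

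A reader might infer that the PSA model is misspecified and its result misleading because PSA responds proportionally. The documents do not support that. The SAP nowhere says that the effect is proportional, and it lists PSA as a safety measure, not as a pharmacodynamic marker. With 1:1 randomisation in large arms, a baseline-adjusted mean difference is a valid average effect even if slopes or spread differ between arms. A percentage description is also planned, in Tables 3.80 and 3.81; what it lacks is an adjusted contrast with an interval.

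On cluster, Appendix 4 ties the countries to efficacy analyses, and the Fisher's exact tests for safety ignore them. That weakens the complaint without removing it: the neighbouring post void residual test in section 8.2.8 does control for cluster, and no reason is given for leaving it out of the PSA model. As for diagnostics, PSA is not alone, since the plan does not extend Appendix 12 to BII, BHS or PAS SFI either.

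**Conclusion.** The point holds as a minor one. PSA is the only pooled general linear model without cluster, and its only planned inference is in ng/mL; percentage change has no adjusted estimate or interval.

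The cost depends on assumptions that the SAP neither makes nor excludes. Under a roughly proportional effect, one figure averages effects up to 6.7-fold apart and efficiency is roughly 45% to 75% of the log-ratio model (assumed ratios 0.5 to 0.9, log SD 0.35). Under an additive effect the raw model is the better one. Cluster matters only if countries differ in PSA change. A reader might conclude that the log-ratio model should replace the planned comparison. Because the listed endpoint is change and the ranking of the models can reverse, the evidence supports adding it alongside, not replacing.

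**What to change.** 1. In section 8.2.7, add cluster to the model for ng/mL change and keep that comparison as the one for the listed endpoint.
2. Add a supportive model at each post-baseline PSA assessment: log(post-baseline PSA / baseline PSA) = log(baseline PSA) + treatment + cluster, as in section 8.1.3. Report the adjusted geometric mean percentage change per arm and the between-arm ratio with its 95% CI. Tables 3.80 and 3.81 could carry these results.
3. Extend the Appendix 12 residual and treatment-by-baseline checks to PSA.

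The cost is SAP wording, one extra model and display per visit, and re-use of the prostate volume program. No new data are needed. The log-ratio result must be labelled supportive, so that a second PSA p-value is not read as a second formal test.

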8.2.8. Post Void Residual Volume

Total voided volume (in conjunction with Qmax) is measured at screening (Visit 1a with possible repeat at Visit 1b), baseline, and at each Month 6, Month 12, Month 18, and Month 24 (or end of treatment) visits.

A list of planned data displays is in [Appendix 15](#): List of Data Displays. Baseline, change from baseline, and percentage change from baseline are defined in Appendix 6. Last observation carried forward (LOCF) and At Visit approaches are defined in Appendix 7. Summaries and analyses will be in terms of the ITT population; LOCF approach will be considered primary. Post void residual volume summary statistics will be presented for each scheduled visit; change from baseline and percentage change from baseline will be presented for each scheduled post-baseline visit.

Post void residual volume change from baseline distribution at each scheduled post-baseline assessment will be compared in terms of combination treatment versus tamsulosin treatment using a nonparametric van Elteren test controlling for cluster at the 0.05 level of significance.

A listing of post void residual volume data will be provided.

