8.1.4. Maximum Urine Flow (Qmax)

Qmax and associated total voided volume are measured at screening (Visit 1a with possible repeat at Visit 1b), baseline, and at each Month 6, Month 12, Month 18, and Month 24 (or end of treatment) visits. Qmax change from baseline is a secondary efficacy endpoint. Qmax measurements with voided volumes <125 ml will not be included in the analysis.

[Table 4](#) provides an overview of the planned Qmax summaries and analyses. A list of planned data displays is in [Appendix 15](#): List of Data Displays. Baseline, change from baseline, and percentage change from baseline are defined in [Appendix 6](#). Last observation carried forward (LOCF) and At Visit approaches are defined in [Appendix 7](#). Summaries and analyses will be in terms of the ITT population; LOCF approach will be considered primary. Qmax summary statistics will be presented for each scheduled visit; change from baseline and percentage change from baseline will be presented for each scheduled post-baseline visit.

Change from baseline Qmax at each scheduled post-baseline assessment will be compared in terms of combination treatment versus tamsulosin treatment using t-tests from a general linear model (GLM) with effects for treatment, cluster, and baseline Qmax. Two-sided tests at 0.05 level of significance will be conducted.

The adjusted mean estimates (mean and standard error), the adjusted mean difference, and the 95% confidence interval in terms of the adjusted mean difference will be presented. The adjusted mean difference will be in terms of combination treatment minus tamsulosin treatment. The model results will be presented on same tabular summary as the arithmetic mean, standard deviation, median, minimum and maximum. The results will be presented by treatment for each scheduled post-baseline assessment.

Qmax adjusted mean change from baseline will be plotted by treatment for each post-baseline scheduled visit in terms of each LOCF and At Visit approach.

Qmax improvement is also assessed using categorical changes. Improvement is a post-baseline Qmax which is higher than the baseline Qmax. Worsening is a post-baseline Qmax which is lower than the baseline Qmax. The number and percentage of subjects with Qmax percentage change from baseline categories of 1) improvement, 2) no change, and 3) worsening will be summarized by treatment group using both the LOCF and At Visit approaches at each scheduled post-baseline assessment.

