11.2. Appendix 2: Time & Events

11.2.1. Protocol Defined Time & Events

Study Procedures	Visit 1a Pre-Screen	Visit 1b** Screening (V1a + 14 days)	Visit 2 Baseline (V1b + 28d ± 4 days)	Visit 3 (Baseline + 13 wks ± 14 days)	Visit 4 (Baseline + 26 wks ± 14 days)	Visit 5 (Baseline + 39 wks ± 14 days)	Visit 6 (Baseline + 52 wks ± 14 days)	Visits 7 - 9 (Years 2, repeat as for V3-V5 of Year 1)	Visit 10 (Baseline + 104 wks ± 14 days)
	Pre-Screen Visit	Start of Placebo run-in	Start of Treatment Phase Baseline (Randomization)	3 months post Randomization (Rand)	6 months post Rand	9 months post Rand	12 months post Rand	15,18 & 21 months post Rand respectively	End of Treatment Phase 24 months post Rand ⁱ
ICF	X								
Inclusion/Exclusion	X	X							
Medical Hx/ Demog/CV Hx/	X								
ECG (12-lead)		X							
Collection of PGx Sample			X						
Safety evaluations									
Concomitant medication	X	X	X	X	X	X	X	⇒	X
Physical Examination ^a		X			X		X	X ^h	X
Vital signs ^b		X	X	X	X	X	X	⇒	X
Haematology/clinical chemistry	X						X		X
HBsAg and Hepatitis C Antibody ^g			X						
Total serum PSA ^c	X				X		X		X
Post-void residual volume (PVR)	X	X***	X		X		X	X ^h	X
AEs ^d		X	X	X	X	X	X	⇒	X
Suicidality (C-SSRS)	X				X		X		X
Efficacy:									
BPH symptoms (IPSS)	X		X	X	X	X	X	⇒	X
Prostate Volume (TRUS)		X					X		X

Study Procedures	Visit 1a Pre-Screen	Visit 1b** Screening (V1a + 14 days)	Visit 2 Baseline (V1b + 28d ± 4 days)	Visit 3 (Baseline + 13 wks ± 14 days)	Visit 4 (Baseline + 26 wks ± 14 days)	Visit 5 (Baseline + 39 wks ± 14 days)	Visit 6 (Baseline + 52 wks ± 14 days)	Visits 7 - 9 (Years 2, repeat as for V3-V5 of Year 1)	Visit 10 (Baseline + 104 wks ± 14 days)
	Pre-Screen Visit	Start of Placebo run-in	Start of Treatment Phase Baseline (Randomization)	3 months post Randomization (Rand)	6 months post Rand	9 months post Rand	12 months post Rand	15,18 & 21 months post Rand respectively	End of Treatment Phase 24 months post Rand ⁱ
Peak Urine Flow (Qmax)	X	X ^{**}	X		X		X	X ^b	X
AUR or BPH-related Surgery			X	X	X	X	⇒	X	X
Pharmacokinetics^j									
Serum PK samples ^j				X	X	X			
Health Outcomes:									
BPH Health Status Q 8 IPSS (BHS)	X		X	X	X	X	X	⇒	X
AUR or BPH-related Surgery Medical Resource Utilisation			X	X	X	X	X	⇒	X
BPH Impact Index (BII)	X		X	X	X	X	X	⇒	X
PAS-SFI		X	X				X		X
Other Efficacy Measures									
UTI /Incontinence / Renal Insufficiency			X	X	X	X	X	⇒	X
Register in RAMOS	X								
Study Medication:									
Call RAMOS/DispenseMeds		X ^e	X ^f	X	X	X	X	⇒	

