
 A subject's baseline date will be the latest non-missing value of either (double-blind) treatment start date or randomization date. Baseline date will be used in the derivation of study day values and Baseline Values. 'Baseline date' may differ from the Visit 2 (Baseline Visit) date recorded in eCRF.
Baseline Value

 For purposes of data analyses, the subject's baseline value of an assessment will be defined as the latest assessment on or before the Baseline Date.
Change and % Change from Baseline

 Change from Baseline = Post-baseline Value – Baseline % Change from Baseline = $100 \times [(\text{Post-baseline Value} - \text{Baseline}) / \text{Baseline}]$

Study Day																				
Study Day is calculated as the number of days from Baseline Date:																				

 • Reference Date = Missing → Study Day = Missing • Reference Date < Baseline Date → Study Day = Reference Date – Baseline Date • Reference Date ≥ Baseline Date → Study Day = Reference Date – (Baseline Date) + 1 																				
Cut-off Dates																				
-Month k Cut-off Date (for k= 3, 6, 9, 12, 15, 18, 21, 24): The maximum of [Month k clinic visit date, Month k lab visit date, Baseline Date + (k * 91/3)].																				
Time Since LUTS First Noted (in years)																				
-Time Since LUTS First Noted = Baseline Date minus Date LUTS First Noted by Patient / 365																				
Time Since BPH Clinical Diagnosis (in years)																				
-Time Since BPH Diagnosis = Baseline Date minus Date of BPH Clinical Diagnosis / 365																				
Age																				
Only year of birth is collected in the eCRF. For purposes of calculating age for a given subject, date of birth will be defined as June 30 th of the corresponding year of birth. Age is calculated in terms of Screening (Visit 1b) date and output as a truncated integer. Age categories include <65, ≥65, <75, and ≥75 years.																				
Body Mass Index (BMI) (kg/sq m)																				
BMI = Weight (kg) / [Height (m)] ²																				
Race / Ethnicity																				
Race / ethnicity will be determined based on a subject's reported ethnicity and geographic ancestry as defined in the following table.																				

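### The planned post-void residual test is valid but leaves out baseline PVR as a covariate, unlike every other formally tested continuous change measure, and so gives up some precision

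*SAP*

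**What the plan says.** Section 8.2.8 fixes both the variable and the test. "Post void residual volume change from baseline distribution at each scheduled post-baseline assessment will be compared" between combination and tamsulosin, "using a nonparametric van Elteren test controlling for cluster at the 0.05 level of significance". LOCF is the primary approach. No baseline covariate or baseline stratum is named, and Appendix 15 lists no baseline-adjusted PVR analysis.

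A baseline value is available. The schedule in Appendix 2 marks PVR at Visit 2 as well as at screening and at Months 6, 12, 18 and 24. Appendix 6 sets the general rule that "the subject's baseline value of an assessment will be defined as the latest assessment on or before the Baseline Date".

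Elsewhere the SAP adjusts continuous changes for baseline. Section 7.1.2 analyses IPSS change with a "general linear model (GLM) with effects for treatment, cluster, and baseline IPSS", and Section 8.1.4 analyses Qmax change with a "general linear model (GLM) with effects for treatment, cluster, and baseline Qmax".

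Section 2.2 lists PVR among the safety endpoints.

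**The concern.** Subtracting baseline forces its slope to 1. For a variable as noisy as a residual volume the true slope is likely to be lower. Raw change then carries the full measurement noise of the baseline reading and over-corrects any chance baseline difference between the arms.

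A skewed variable is a good reason for a rank test, but not for dropping the covariate, because rank-based covariance analysis is available. At stake is the power to see a difference in residual volume. This matters somewhat more for a safety measure, where a non-significant result may be taken as reassurance.

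**Working it through.** **1. How the SAP treats its other tested continuous changes**

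| Measure (SAP section) | Baseline as covariate | Cluster term |
|---|---|---|
| IPSS (7.1.2) | yes | yes |
| Prostate volume, log ratio (8.1.3) | yes, log baseline | yes |
| Qmax (8.1.4) | yes | yes |
| PSA (8.2.7) | yes | no |
| BII (8.3.1) | yes | yes |
| BHS (8.3.2) | yes | yes |
| PAS SFI (8.3.3) | yes | yes |
| PVR (8.2.8) | **no** | yes |

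All seven others are adjusted. Laboratory and vital-sign changes are summarised without a test of the mean change. The remaining tests that omit baseline concern proportions or events.

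**2. Normal-theory size**

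The SAP states no SD, correlation, effect or power for PVR, so there is no figure to reproduce. Assume equal variance σ² at baseline and follow-up, and correlation ρ.

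- Variance of raw change: 2σ²(1−ρ)
- Residual variance after baseline adjustment: σ²(1−ρ²)
- Ratio: (1−ρ²) / [2(1−ρ)] = (1+ρ)/2
- Extra patients needed by raw change for equal precision: 2/(1+ρ) − 1

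| Assumed ρ | Variance ratio | Extra patients |
|---|---|---|
| 0.2 | 0.60 | 67% |
| 0.3 | 0.65 | 54% |
| 0.4 | 0.70 | 43% |
| 0.5 | 0.75 | 33% |
| 0.6 | 0.80 | 25% |
| 0.7 | 0.85 | 18% |
| 0.9 | 0.95 | 5% |

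Expressed as power: if the effect is set so that the adjusted analysis has 80% power, raw change has Φ[(1.960 + 0.842)·√((1+ρ)/2) − 1.960]. This gives 61.7%, 67.9% and 73.3% at ρ = 0.3, 0.5 and 0.7.

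**3. Rank-based check on skewed data**

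Because the planned test is a rank test, the comparison was simulated directly. All settings are assumed: lognormal PVR, four strata, 300 per arm, a shift of 0.2 SD on the log scale, and 1,500 replicates.

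| Assumed ρ | van Elteren on change | Rank ANCOVA, change given baseline | Rank ANCOVA, follow-up given baseline |
|---|---|---|---|
| 0.3 | 43.3% | 57.5% | 69.1% |
| 0.5 | 54.8% | 66.3% | 76.0% |
| 0.7 | 77.5% | 83.9% | 90.2% |

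The gain over van Elteren is 6 to 14 points if change is still the ranked variable, and 13 to 26 points if the follow-up value is ranked. With no treatment effect, all three methods rejected in 4.1% to 5.9% of replicates, against a simulation standard error of about √(0.05×0.95/1500) = 0.6 points.

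**The case against.** The strongest reply is that nothing in 8.2.8 is wrong. The variable, test, stratification, level and missing-data approach are all stated. A van Elteren test is a defensible choice for a skewed variable, and it held its level in the simulation. That stands, and it limits the point to efficiency.

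Several stronger readings are tempting, and the SAP does not support them:

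- **That the comparison is biased or invalid.** Chance baseline imbalance averages out under randomization.
- **That PVR is the only tested change left unadjusted.** This is true only of continuous measures. The improvement-level comparisons for IPSS, prostate volume and Qmax (8.1.2 to 8.1.4) are Mantel-Haenszel tests controlling for cluster alone. The breast-examination and DRE shifts (8.2.9, 8.2.10) use unadjusted Fisher tests.
- **That 67% is the size of the loss.** It is the low-correlation end of an assumed range, from a formula for parametric analyses with equal variances. At ρ = 0.9 the figure is 5%.
- **That urinary retention is poorly assessed.** Section 8.1.5 analyses acute urinary retention in its own right, with stratified log-rank, Cox and crude-rate comparisons.

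It is also fair to say that ranking the follow-up value changes what is tested, because 8.2.8 speaks of the distribution of change. In a linear model with baseline as covariate the two choices give the same treatment contrast; with ranks they do not. About half or more of the larger simulated gain comes from adding baseline, and the rest from this switch.

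**Conclusion.** The point holds as a matter of efficiency. Section 8.2.8 leaves out a covariate that is already in the data and that the SAP uses for all seven comparable measures, without giving a reason. The cost is power and precision only: a variance ratio of 0.60 to 0.85 for assumed ρ of 0.2 to 0.7, shrinking to nothing as ρ nears 1. The skewed-data simulation agrees in direction, but its figures depend on its assumed distribution, effect and sample size.

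The consequence is small. PVR is one of several safety endpoints. Under Appendix 11 the primary IPSS test comes first and the secondary endpoints have no order among them, so no other endpoint's test waits on the PVR result. The change is minor and optional, and the primary conclusion is unaffected either way.

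**What to change.** In Section 8.2.8, make the PVR comparison a cluster-stratified rank ANCOVA with baseline PVR as covariate. Within each cluster, rank the post-baseline measure and baseline PVR, regress the first ranks on the second, and compare the residuals between arms with the stratified mean-score test. State before unblinding whether the follow-up value or the change is ranked. Ranking change stays closer to the present text; ranking follow-up gained more in the simulation. Keep the van Elteren test as a supportive check.

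For the country-specific package in Section 9, the same method applies without the cluster strata.

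The cost is a sentence or two in the SAP and a few lines of SAS. No new data are needed.
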